We propose to conduct a prospective evaluation of the use of Omegaven™ for the provision of parenteral lipid calories in concert with an active ongoing program of intestinal rehabilitation. Our main outcome of interest will be need for small bowel transplantation, with secondary outcomes including improvement in clinical measures associated with PNALD and need for liver transplantation. This study will be conducted in both pediatric and adult intestinal rehabilitation patients.

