### Objectives

The primary objective of this study is to evaluate the need for small bowel transplantation. Clinical data will be collected prospectively and will be compared with historical controls.

Secondary objectives are to determine if there are improvements in clinical measures associated with established parenteral nutrition- associated liver disease (PNALD).

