## **Study Design**

This study will be a prospective, non-randomized, open-label study of Omegaven™ with a total enrollment of 100 patients, for provision of parenteral lipid calories. The study cohort, receiving the PN at 1g/kg/day, will be compared to historical controls at UNMC where parenteral lipid calories were provided exclusively through soybean-based formulations, as well as, assessing the study cohorts need for small bowel and liver transplantation.

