#### **2. Evaluation**

During this period, the Investigator will evaluate to confirm eligibility. All these procedures are performed at initial evaluation on all patients in the Intestinal Rehabilitation Program, regardless of entry into a study. In addition to a review of body systems, the baseline evaluations will include the recording of body weight and routine urine and blood laboratory analyses. These blood and urine analyses will determine vitamin, trace element, essential fatty acid levels, serum electrolytes, hydration status, kidney function and liver function. Patients will also have radiology and GI exams. It is possible the evaluation may include a liver biopsy. The patient's pre-study TPN prescription will also be recorded.

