## Statistical Analysis

Data from the two sets of patient population will be pooled and compared (i.e., current protocol patients prescribed Omegaven™ PN compared to historical controls where parenteral lipid calories were provided exclusively through soybean-based formulations). Potential for effect in different patient populations will be minimized by matching patients enrolled in the Omegaven™ protocol to historical controls. Frequency matching will be utilized given the difficulty of paired matching in this patient population. Specific matching criteria will include gender, age, etiology of short bowel syndrome, and severity of liver disease (parenteral nutrition- associated liver disease).

Continuous data will be expressed as mean +/- SEM. A two-way repeated measure ANOVA will be used to compare differences in the two groups with respect to changes between the Evaluation assessment and the subsequent analyses performed at Treatment and Treatment/Follow-up Assessments. Incidence of adverse events in each treatment arm will be compared using Fisher's exact test. Univariate and multivariate analysis will be used to identify baseline factors that may influence outcome. A P-value <0.05 will be considered statistically significant.

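### Baseline PN dependence is neither matched nor adjusted for in the comparison with historical controls, and the controls have no stated PN-need criterion or common start of transplant follow-up

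*Combined protocol and SAP*

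**What the plan says.** The Objectives section states: "The primary objective of this study is to evaluate the need for small bowel transplantation", with comparison to historical controls. The study is non-randomised and open-label with 100 Omegaven patients. Background and Rationale adds: "This study will be conducted in both pediatric and adult intestinal rehabilitation patients".

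Study Design defines the comparison group as "historical controls at UNMC where parenteral lipid calories were provided exclusively through soybean-based formulations", and Statistical Analysis repeats this definition. Neither section gives a number of controls, an eligibility rule beyond site and lipid source, or a date from which a control is followed.

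Statistical Analysis plans frequency matching and says: "Specific matching criteria will include gender, age, etiology of short bowel syndrome, and severity of liver disease". On analysis it says: "A two-way repeated measure ANOVA will be used to compare differences in the two groups", and this is "with respect to changes between the Evaluation assessment and the subsequent analyses". No covariates are listed and no test is named for transplantation. It then says: "Univariate and multivariate analysis will be used to identify baseline factors that may influence outcome".

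The 2. Evaluation section records each patient's TPN prescription from before the study. Evaluation Assessments lists PN days, volume, calories, protein and lipid per week, together with body weight. Inclusion Criteria asks enrolled patients for an expected further PN need of at least 30 days and a direct bilirubin of at least 2 mg/dL.

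**The concern.** Without randomisation, the transplant comparison is only as good as the comparability of the two groups. The program's own aim is to get patients off PN, so how far a patient depends on PN at the start is a natural candidate for a strong predictor of transplant need. None of the four named factors measures it, and etiology of short bowel syndrome captures it only in part.

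If the controls were more PN-dependent than the Omegaven patients, transplantation could look less frequent on Omegaven with no drug effect. If they were less dependent, a real benefit could be hidden. If the adjusted model is chosen only after the data are seen, a reader cannot tell which group estimate was planned.

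The same applies to who counts as a control and when the clock starts. An expected PN need of 30 days is a prognostic filter, and it is written for one group only.

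**Working it through.** **1. Is PN dependence covered anywhere?**

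| Place in the plan | What it commits to | PN dependence covered? |
|---|---|---|
| Matching list | gender, age, etiology, liver severity | No; etiology is a partial proxy |
| Repeated-measures ANOVA | change from Evaluation, two groups | No covariates; concerns change measures, not transplantation |
| Univariate and multivariate analysis | finding baseline factors | Possible, but no covariate and no adjusted group effect is named |
| Definition of controls | UNMC, soybean-only lipid | PN exposure is implied; degree and expected duration are not |
| Inclusion Criteria | 30 more days of PN, direct bilirubin | Written for enrolled patients only |

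**2. Is a start date given for controls?** The nearest text is in 2. Evaluation: "All these procedures are performed at initial evaluation on all patients in the Intestinal Rehabilitation Program, regardless of entry into a study". Read with the ANOVA sentence, it suggests a laboratory baseline for controls who were in the program. It is not linked to the controls or to the start of transplant follow-up in either group.

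**3. How much could an imbalance matter?** The plan gives no power, event rate or control count, so there is no figure to reproduce. What follows is an illustration. The only input from the documents is 100 Omegaven patients. Assumed: 100 controls, a two-sided 5% Fisher test (no transplant test is named and sidedness is not stated), transplantation counted as yes or no, and a binary high/low PN-dependence factor.

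Group risk = s × h + (1 − s) × l, where s is the share with high PN dependence and h and l are the transplant risks at high and low dependence. With no drug effect, the spurious difference is (s in controls − s in Omegaven) × (h − l).

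For example, strong factor, 20-point imbalance: Omegaven 0.40 × 0.40 + 0.60 × 0.10 = 0.22; controls 0.60 × 0.40 + 0.40 × 0.10 = 0.28; difference 0.20 × 0.30 = 0.06.

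| High-PN share, Omegaven v controls | Strong factor (40% v 10%): risks | False benefit | Weak factor (30% v 20%): risks | False benefit |
|---|---|---|---|---|
| 50% v 50% | 25% v 25% | 1.7% | 25% v 25% | 1.7% |
| 45% v 55% | 23.5% v 26.5% | 5.1% | 24.5% v 25.5% | 2.5% |
| 40% v 60% | 22% v 28% | 12.6% | 24% v 26% | 3.6% |
| 40% v 70% | 22% v 31% | 24.9% | 24% v 27% | 5.1% |

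False benefit is the exact probability that Fisher's test is significant in favour of Omegaven. In the strong-factor, 30-point case it is about 19% with 50 controls and 35% with 200.

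**Opposite direction.** Suppose Omegaven truly halves the risk and the strong factor is unbalanced against it. Power is 56% when balanced (12.5% v 25%), 40% with a 10-point imbalance (13.25% v 23.5%) and 25% with 20 points (14% v 22%).

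**4. Does adjustment help?** Logistic simulation, 100 v 100, strong factor, no drug effect, Wald test. False benefit for imbalances of 10, 20 and 30 points:

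- unadjusted: about 7%, 16% and 30%;
- adjusted, PN dependence measured without error: about 2.5% throughout;
- adjusted, 10% of patients misclassified: about 4%, 6% and 8%;
- adjusted, 20% misclassified: about 5%, 9% and 16%.

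Adjustment removes much of the problem but not all of it.

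**The case against.** The strongest reply is that the numbers describe assumptions, not this trial. The larger figures need a fourfold risk ratio and a 20- to 30-point imbalance that survives matching on age, etiology and liver severity. The illustration does not model that matching, and nothing in the documents supports an imbalance of that size. With a weak factor the false-benefit rate stays between 2.5% and 5.1%. This stands, and it is why no single size can be claimed.

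The matching list is also open-ended, and the multivariate analysis could take in PN measures. Both are true, but permission is not a commitment. The stated purpose of that analysis is to find baseline factors, not to give an adjusted comparison.

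Four stronger readings are tempting, and the documents do not support them:

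- **That controls might not have been on PN.** They received parenteral lipid, and severity matching is on PN-associated liver disease. What is missing is the degree and expected duration of PN need.
- **That the covariate-free ANOVA biases the transplant result.** It concerns change measures. For transplantation the gap is that no adjusted estimate is planned.
- **That a later start of follow-up favours Omegaven.** No lag or hazard pattern is given, so no direction can be derived.
- **That the Abstract and Inclusion Criteria conflict on bilirubin.** One says whom to approach and the other who is eligible; they can be read in sequence.

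**Conclusion.** The concern holds in a limited form. The plan does not commit to controlling baseline PN dependence in a non-randomised comparison, although the variable is already collected for the Omegaven cohort. It does not apply the PN-need and direct bilirubin criteria to the controls, and it fixes no common start of transplant follow-up.

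Size and direction are unknown. With 100 controls, the assumed inputs span a false-benefit rate from near the nominal 2.5% per direction to about 25%, and an opposite imbalance can cost power instead. That PN dependence predicts transplantation is itself an assumption, though one in line with the program's aim of ending PN. A reader might infer that the planned comparison is biased towards Omegaven, or that its error rate is 25%; neither follows. The point is worth correcting because the remedy is specific and inexpensive, not because harm has been shown.

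**What to change.** **Statistical Analysis.** Keep frequency matching. Name as the primary Omegaven-versus-control estimate for transplantation an adjusted group effect that includes the matching factors, baseline direct bilirubin and one baseline PN measure already collected. An example is PN kcal/kg/day, obtained from weekly PN calories and body weight. Age belongs in the model because children and adults are mixed. If transplants are too few for that many terms, use a propensity score built from the same variables. Report baseline PN by group.

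**Study Design and Statistical Analysis.** Select controls by the bilirubin and PN-need criteria of Inclusion Criteria at a defined index date, using only chart information available on that date. Using the later PN course would bring in hindsight selection or immortal time. Require controls to be transplant-free at the index date and soybean-only up to it. Start the transplant clock by the same rule in both groups. Compare over the same fixed follow-up window or by a time-to-event method, with death before transplant handled as a competing event.

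**Cost.** SAP wording, plus chart abstraction of PN prescription, weight, bilirubin and expected PN need for controls; whether past charts hold these is an assumption. There may be fewer eligible controls and some loss of precision. Residual confounding will remain, because any single PN measure captures dependence imperfectly.

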## BACKGROUND AND RATIONALE

Patients with intestinal failure are unable to support growth or maintain health without some provision of nutrition parenterally. The Intestinal Rehabilitation Program at the University of Nebraska Medical Center is a multidisciplinary team focused on achieving enteral nutritional independence through optimization of intestinal function and autologous reconstruction of the GI tract. The program functions, along with small bowel transplantation, as part of the comprehensive intestinal failure program at UNMC. Many of our patients have excellent bowel rehabilitation potential given sufficient time for reconstruction and intestinal adaptation, but are limited by concurrent progression of parenteral nutrition-associated liver disease (PNALD). The ability to slow or reverse PNALD may dramatically impact on our ability to treat intestinal failure.

Lipids are necessary in PN dependent patients due to their high caloric value and essential fatty acid content. In the United States, most patients dependent upon PN receive parenteral fat emulsions composed of soybean oils, which have been implicated in predisposing patients to PN-associated liver disease (PNALD). There is evidence in the scientific literature supporting use of lipid formulations comprised mainly of omega-3 fatty acids to halt or reverse the progression of PNALD (Gura, 2008; Diamond, 2009). It is believed that fish oil-based formulations such as Omegaven™ mediate reduction of liver injury through inhibition of de novo lipogenesis, reduction of arachidonic acid-derived inflammatory mediators, and improved clearance of lipids from the serum. Animal studies have shown that IV fat emulsions (IFE), such as fish oil that are high in eicosapentaenic and docosahexaenoic acid, educe impairment of bile flow which is seen in cholestasis caused by conventional fat emulsions (Alwayn, 2005; Van Aerde, 1999). By administering Omegaven™ in place of conventional soybean fat emulsions we hope to reverse or prevent the progression of PNALD, allowing sufficient time for intestinal rehabilitation and eventual cessation of parenteral nutrition.

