## **Inclusion Criteria**

The first 100 eligible patients must meet the conditions listed below:

- Patients must be enrolled in the Intestinal Rehabilitation Program at the University of Nebraska Medical Center, and:
- Be unable to meet nutritional needs solely by enteral nutrition and be expected to require PN for at least another 30 days
- Have clinical evidence of parenteral nutrition associated liver disease (PNALD) as defined as direct bilirubin of 2mg/dl or more. A liver biopsy is not necessary for treatment.
- Signed patient informed consent.

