### **Side Effects (that may lead to Disruption or Discontinuation of Omegaven™):**

The infusion of Omegaven™ can lead to prolonged bleeding time and an inhibited platelet aggregation. The administration of Omegaven™ should be stopped or reduced if there is a marked increase in blood glucose levels during infusion. Undesirable effects that are seen during infusion of Omegaven™ that may also occur with conventional fat emulsions (i.e., Intralipid) include:

Slight rise in body temperature, Heat sensation and/or cold sensation, Chills, Dyspnea, Flushing or cyanosis, Lack of Appetite, nausea, vomiting, Headache, pain in chest, bone pain, Priapism, Increase/decrease in blood pressure, Anaphylactic reactions/erythema

Other expected adverse events that are common to all patients with short bowel syndrome, regardless of the type of fat emulsion they receive, include blood stream infections and re-admittance to hospital. Causes for re-hospitalization include dehydration, bloodstream infections, electrolyte abnormalities, bowel obstruction, and central venous catheter malfunction.

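### The matching plan has no level for patients without short bowel syndrome and no factor for remaining bowel or PN dependence, so transplant risk could differ between groups for reasons other than Omegaven

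*Combined protocol and SAP*

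**What the plan says.** Under Objectives, the primary aim is need for small bowel transplantation, compared with historical controls. Study Design describes a non-randomized, open-label cohort of 100, with UNMC controls who received only soybean-based lipid.

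Comparability is to come from matching, described in Statistical Analysis: "Specific matching criteria will include gender, age, etiology of short bowel syndrome, and severity of liver disease". The matching is at group level: "Frequency matching will be utilized given the difficulty of paired matching in this patient population". The same section plans univariate and multivariate analyses to find influential baseline factors.

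The Inclusion Criteria define the treated cohort by program membership, PN dependence and bilirubin, in addition to consent. Membership is stated first: "Patients must be enrolled in the Intestinal Rehabilitation Program at the University of Nebraska Medical Center". The PN condition is functional and sets no anatomical requirement: "Be unable to meet nutritional needs solely by enteral nutrition and be expected to require PN for at least another 30 days". The third condition concerns the liver and rests on a laboratory threshold: "Have clinical evidence of parenteral nutrition associated liver disease (PNALD) as defined as direct bilirubin of 2mg/dl or more".

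None of these is a diagnosis of short bowel syndrome, and the Exclusion Criteria remove no other cause of intestinal failure.

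**The concern.** The matching factor describes a narrower population than the one enrolled. A patient who is PN-dependent for another reason, such as a motility or mucosal disorder, has no short-bowel etiology. The plan does not say whether that patient is dropped, left unmatched or put in a residual category.

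The matching factors also omit the bowel itself. Two groups could agree on sex, age, etiology and liver disease severity and still differ in how much bowel remains or how far patients depend on PN. If that affects the chance of leaving PN without a transplant, the difference would be credited to, or counted against, Omegaven. With no randomization, only matching or adjustment can prevent this.

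**Working it through.** **Text check**

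1. *Population.* Background and Rationale speaks of intestinal failure in general: "Patients with intestinal failure are unable to support growth or maintain health without some provision of nutrition parenterally". Short bowel syndrome is presumed only in passing, under Side Effects: "Other expected adverse events that are common to all patients with short bowel syndrome, regardless of the type of fat emulsion they receive". It is never an entry condition.
2. *Relevance of the bowel.* Background and Rationale states: "Many of our patients have excellent bowel rehabilitation potential given sufficient time for reconstruction and intestinal adaptation". The sentence then names progression of PNALD as what limits these patients. The protocol thus brings both bowel potential and liver disease to bear on outcome. Only liver disease severity is matched.
3. *Data available.* Evaluation Assessments lists PN requirement (days, volume, calories, protein, lipid), citrulline, 24-hour intake and stool volume, small bowel follow-through and barium enema. It does not list remaining bowel length, ileocecal valve or colon in continuity. No listed item is assigned to matching or adjustment.
4. *Adjustment.* The multivariate sentence names no covariates and states no adjusted comparison of the groups. No test is specified for transplantation at all: the repeated-measures ANOVA is for changes from Evaluation, and Fisher's exact test is for adverse events.

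The plan has no figure to reproduce here. The enrollment of 100 comes without a transplant rate, effect size, power or number of controls.

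**Illustration 1: short-bowel case mix (all inputs assumed)**

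- Non-short-bowel share: 5–20% of the cohort, 20–30% of controls.
- Transplant risk: 50–60% without short bowel syndrome, 25% with it.
- Shift in the difference = (control share − cohort share) × (risk without − risk with).
- Smallest: (0.20 − 0.20) × (0.50 − 0.25) = 0 points.
- Largest: (0.30 − 0.05) × (0.60 − 0.25) = 0.25 × 0.35 = 8.75 points.

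The direction is built into the assumed shares. If the cohort had more non-short-bowel patients than the controls, the sign would reverse.

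**Illustration 2: an unmatched bowel factor (all inputs assumed)**

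Take 100 patients per group, no drug effect, and a two-sided pooled z-test of two proportions at 0.05. The documents give neither the number of controls nor this test.

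- Risk 0.40 with unfavourable bowel and 0.20 with favourable; unfavourable share 60% of controls and 40% of treated. Controls: 0.6 × 0.40 + 0.4 × 0.20 = 0.32. Treated: 0.4 × 0.40 + 0.6 × 0.20 = 0.28. Spurious difference 4 points; false-positive rate 9.4%.
- Risks 0.50 and 0.10, same shares. Controls 0.34, treated 0.26. Spurious difference 8 points; false-positive rate 23.4%.
- From risks 0.30/0.20 with shares 55%/45% up to risks 0.60/0.10 with shares 65%/35%: 1 to 15 points, false-positive rate 5.3% to 60.5%.
- Equal shares: no bias, 5.0%.

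For scale, 100 against 100 with 80% power detects a fall from 20% to 6.6%, 30% to 13.7%, 40% to 21.7% or 50% to 30.6%, that is, about 13 to 19 points. The bias is small beside these in the mild scenarios and comparable in the severe ones.

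**The case against.** The other side has several fair points.

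- *PNALD is the stated limit, and it is matched.* This stands. A reader might infer that remaining bowel is the main driver of transplantation or that rehabilitation potential is decisive. The documents say neither. They support only the bowel as a plausible prognostic factor beside liver disease.
- *Non-short-bowel patients could form a residual level of etiology.* That is a natural reading. If applied in both groups, it would remove the bias in Illustration 1. The plan does not state it, and it would not balance remaining bowel among patients with the same etiology.
- *The list may be open, and etiology may partly reflect anatomy.* Possibly. But an open list lets factors be chosen after control outcomes are known, and partial correlation is not balance.
- *The multivariate analysis is where such covariates would enter.* It could be, but as written it only looks for influential factors.
- *More matching factors would thin the strata.* This stands. Three two-level anatomical factors would split each existing cell into 2 × 2 × 2 = 8, with only 100 treated patients. It argues for covariates instead of further matching.

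A reader might also infer that the comparison is biased in Omegaven's favour. The documents give no case mix for either group, so they do not support a direction.

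**Conclusion.** The point holds in a limited form. The etiology factor does not cover everyone eligible, no matching factor reflects remaining bowel or PN dependence, and no adjusted comparison is stated for the primary outcome. The groups could therefore differ in transplant risk apart from Omegaven.

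The size cannot be found from the documents. The 0 to 8.75 points for case mix and the 1 to 15 points for an unbalanced bowel factor rest entirely on assumed shares and risks; the second range also assumes 100 controls. They show that the bias could be nil or could approach a detectable effect, not that it is present. This is a gap to close before controls are selected, not evidence that the comparison will fail.

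**What to change.** 1. Replace the etiology factor with *cause of intestinal failure*, with levels for the short-bowel etiologies and for non-short-bowel causes. If only short bowel syndrome was intended, the eligibility text and the matching text need to be reconciled.
2. Specify the transplant comparison, which is currently absent, and make it an adjusted one. Pre-specify baseline PN requirement as a covariate. It is already recorded for the cohort, and the Evaluation section describes its evaluation procedures as routine for all program patients. Whether the historical controls have the same data should be confirmed.
3. Where charts in both groups allow, add remaining small-bowel length, ileocecal valve and colon in continuity as covariates, not as further matching strata. Keep the number of covariates in proportion to the number of transplants.
4. Report missingness of bowel anatomy by group, and run a sensitivity analysis adjusting for baseline PN requirement alone.

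The cost is SAP wording and chart abstraction, with no new procedure for patients. The main downside is that older control charts may lack bowel anatomy. Missing data concentrated in one group would weaken that adjustment and could add bias of its own, which is why item 4 is needed.

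### The control rule applies neither the trial's entry criteria, nor a calendar window, nor an index date, so era and selection differences cannot be separated from an Omegaven effect on transplantation

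*Combined protocol and SAP*

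**What the plan says.** The Study Design section describes a "prospective, non-randomized, open-label study of Omegaven™ with a total enrollment of 100 patients". The comparator is "historical controls at UNMC where parenteral lipid calories were provided exclusively through soybean-based formulations". The Objectives section makes need for small bowel transplantation the primary objective and refers the collected data to those controls.

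The Statistical Analysis section adds the matching rule: "Specific matching criteria will include gender, age, etiology of short bowel syndrome, and severity of liver disease". It explains the method: "Frequency matching will be utilized given the difficulty of paired matching in this patient population". The measure of liver disease severity is not defined. The same section plans univariate and multivariate analysis to find baseline factors related to outcome, and sets significance at P<0.05.

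For treated patients the Inclusion Criteria are explicit. "Patients must be enrolled in the Intestinal Rehabilitation Program at the University of Nebraska Medical Center", their direct bilirubin must be at least 2 mg/dl, and each must "Be unable to meet nutritional needs solely by enteral nutrition and be expected to require PN for at least another 30 days". The Exclusion Criteria also remove families or children who cannot or will not follow the program's recommendations.

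No section applies these criteria to controls, or gives a calendar window, an index date or a number of controls.

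**The concern.** With no concurrent group, any causal reading of the transplant result rests on how the controls are chosen. Three routes to a difference without a drug effect are left open.

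- **Era.** Controls are earlier by definition, and nothing limits how much earlier. The Background section describes a rehabilitation program that works toward enteral independence alongside transplantation, so a change in that program or in transplant practice bears directly on the primary outcome. Treated patients must be in the program. Controls need not be.
- **Selection.** Treated patients pass a bilirubin threshold, a forecast of continued PN need and a willingness filter. Controls pass none of these explicitly.
- **Time zero.** The 30-day criterion is a forecast made at enrollment. A chart shows what happened, not what was expected. If a chart reviewer substituted observed PN of 30 days or more, controls would be guaranteed 30 event-free days.

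These routes need not push the same way. Better rehabilitation over time would favour Omegaven, while the 30-day substitution would favour controls. The primary result could mislead in either direction, and the plan offers no means of telling which.

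**Working it through.** **Step 1. Compare the two entry rules.**

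| Requirement | Treated patients | Controls |
|---|---|---|
| UNMC | Yes | Yes |
| Program enrollment | Yes | Not stated |
| Direct bilirubin at least 2 mg/dl | Yes | Not stated; severity matched, measure undefined |
| Expected PN for 30 more days | Yes | Not stated |
| Willing and able to follow the program | Yes | Not stated |
| Calendar window | Enrollment period | Not stated |
| Start of follow-up | Treatment, after evaluation and consent | Not stated |

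Frequency matching balances the distribution of a factor between groups. It does not impose a threshold on each control, and it does nothing for factors that are not on the list.

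**Step 2. Size of a false signal from era or selection.** The plan gives no transplant rate, number of controls, power calculation or test for the transplant outcome, so there is no planned figure to reproduce. Assumed inputs: 100 treated (the stated enrollment), 100 controls, no drug effect, two-sided 0.05, true control rate p₁ = 40%, and treated rate p₂ lowered by era alone.

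The z-test rejects when |x₁ − x₂|/100 exceeds 1.96 × √[p̄(1 − p̄)(2/100)], where p̄ = (x₁ + x₂)/200. The rejection probability is the sum of Bin(x₁; 100, p₁) × Bin(x₂; 100, p₂) over all rejecting pairs. The same sum was taken with Fisher's exact test, the only categorical test the plan names (for adverse events).

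| p₁ v p₂ | z-test | Fisher's exact test |
|---|---|---|
| 40% v 40% | 5.1% | 3.6% |
| 40% v 35% | 11% | 9% |
| 40% v 30% | 32% | 26% |
| 40% v 25% | 63% | 56% |

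Hand check of 40% v 30% by normal approximation: p̄ = 0.35; null SE = √(0.35 × 0.65 × 0.02) = 0.0675; alternative SE = √(0.24/100 + 0.21/100) = 0.0671. Then Φ[(0.10 − 1.96 × 0.0675)/0.0671] = Φ(−0.48) = 0.316.

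**Step 3. Sensitivity to the assumptions.** By the same approximation, with control rates of 20% to 50% and 50 to 200 controls, a 5-point shift gives about 9% to 17%, a 10-point shift 22% to 60%, and a 15-point shift 42% to 96%.

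**Step 4. Size of the 30-day effect, if that substitution were made.** With constant hazard and 12-month risk r, the share of patients with an event in the first 30 days is 1 − (1 − r)^(30/365). For r = 30% this is 1 − 0.70^0.0822 = 2.9%. For r = 50% it is 1 − 0.50^0.0822 = 5.5%. These patients would be missing from the control group only, which makes controls look better.

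**The case against.** The plan is not blind to the problem. It says that matching is meant to reduce population differences, keeps controls to the same center and to one lipid type, and matches on liver disease severity, which partly stands in for the bilirubin criterion. The list of factors is worded as open, and multivariate analysis is planned. A historical-control design is declared openly, and residual era confounding comes with it.

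Some of this stands. The center and soybean limits are real, severity matching helps, and no rewording will remove era confounding. But neither limit fixes the period, and the soybean restriction may itself select earlier patients. No factor beyond the four is named, and an open list leaves room to choose controls afterwards. The multivariate analysis is described as a search for prognostic factors, not as adjustment of the group comparison, and calendar time is not mentioned.

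A reader might infer that the result will be a false Omegaven benefit. The documents do not support that. They contain no transplant rate and no trend over time, and one of the plausible biases runs against Omegaven. Nor do they propose replacing the 30-day forecast by observed duration; that is only something the silence permits.

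**Conclusion.** The point holds as a gap in the control rule: era and selection differences cannot be separated from a drug effect on the primary outcome. It does not hold as a prediction of which way the result will be wrong, or by how much.

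The rejection probabilities in the working rest on assumed transplant rates, an assumed number of controls and an assumed test. They show that a modest shift of 5 points roughly doubles the nominal 5% error by z-test, and that 10 or 15 points would dominate it. They do not show that such a shift exists. The 2.9% to 5.5% figure rests on an assumed annual risk and a constant hazard, and applies only if controls are selected on observed PN duration. The change is worth making before controls are selected, because part of the problem can be removed at low cost.

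**What to change.** In the Statistical Analysis section:

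1. Take consecutive Intestinal Rehabilitation Program patients from the most recent window before Omegaven use began, and state its dates.
2. Require controls to meet the Inclusion Criteria, and those Exclusion Criteria that a chart can show, at a defined index date. Judge the 30-day PN expectation only from information available on that date.
3. Make time zero comparable. Simply indexing controls at their first qualifying bilirubin would start them earlier in their disease than treated patients, who begin only after evaluation and consent and must have remained untransplanted until then. In both groups, record the time from first direct bilirubin of 2 mg/dl or more on PN to the index date or treatment start, and match or adjust for it.
4. Report the calendar year of controls, and run a day-30 landmark analysis in both groups from the aligned time zero as a sensitivity analysis.
5. State that residual era confounding limits the conclusion, since even the most recent window is wholly earlier than the trial.

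The cost is wording in the analysis section and some chart abstraction beyond what finding controls already needs. The downside is possibly fewer controls, and so less precision.
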